1.2.3. Intervention Groups and Duration

There are 5 cohorts planned in this sub-study.

Table 3: Intervention Groups

Cohort	Study Drug	Dose	Route	Number of Doses	Frequency of Dosing
1a	VIR-3434	300 mg	SC	12	Every 4 weeks
	TDF	300 mg ^b	Oral	\geq 308 ^c	Every day
2a	VIR-3434	Up to 300 mg ^a	SC	12	Every 4 weeks
	TDF	300 mg ^b	Oral	\geq 308 ^c	Every day
3a	VIR-3434	300 mg	SC	4-6 ^d	Every 8-12 weeks ^d
	TDF	300 mg ^b	Oral	\geq 252 ^c	Every day
4a	VIR-3434	300 mg	SC	12	Every 4 weeks
	VIR-2218	200 mg	SC	12	Every 4 weeks
	TDF	300 mg ^b	Oral	\geq 308 ^c	Every day
5a	VIR-3434	300 mg	SC	13	Every 4 weeks
	VIR-2218	200 mg	SC	13	Every 4 weeks
	PEG-IFN α	180 mcg	SC	48	Every week
	TDF	300 mg ^b	Oral	\geq 336 ^c	Every day

^a The dose of VIR-3434 will be determined before participants are enrolled in the cohort.

^b Tenofovir disoproxil fumarate dose (TDF) will be 300 mg as approved by the FDA. Supply outside the United States may be Tenofovir disoproxil (TD) 245 mg.

^c The minimum number of doses received by participant. Participants will continue receiving additional doses of TDF until they qualify for NRTI discontinuation.

^d The dosing regimen will be finalized before participants are enrolled in the cohort.

The total duration in the study for participants will be up to 100 weeks in cohorts 1a, 2a, and Cohort 4a, 92-96 weeks for Cohort 3a, and 104 weeks for Cohort 5a. This includes a Screening Period (up to 56 days or 8 weeks), Treatment Period (44 weeks for cohorts 1a and 2a, 36 or

40 weeks for Cohort 3a, 44 weeks for Cohort 4a, and 48 weeks for Cohort 5a) and a Follow-Up Period (up to 48 weeks) for all cohorts.

Once participants complete the Treatment Period per their respective cohort, they will enter the Follow-Up Period. Participants will discontinue the NRTI at the F1 or F12 visit in the Follow-Up Period if they meet the criteria to discontinue NRTI ([Section 1.2.4](#)) based on the data available. Additional study visits are required for participants who discontinue NRTI in the Follow-Up Period as indicated in the SOA in the study protocol. Participants who discontinue NRTI at F1 visit will be required to return to the site for additional visits at F2, F6, F10, F28, F32, F40, and F44. Participants who discontinue NRTI at F12 visit will be required to return to the site for additional visits at F14, F18, F22, F28, F32, F40, and F44.

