1.2.4. NRTI Discontinuation

Participants will discontinue NRTI at F1 or at F12 Follow-Up visits based on the most recent data available if they meet all of the following criteria:

- HBsAg < LLOQ
- Suppressed HBV DNA (defined as < LLOQ)
- Undetectable HBeAg (based on quantitative HBeAg)
- ALT \leq 2 times the upper limit of normal (ULN).

Participants who meet the criteria to discontinue NRTI treatment will continue to be followed? per the Follow-Up Period SOA. Participants who meet NRTI discontinuation criteria but are not appropriate for NRTI discontinuation due to other reasons, based on the opinion of the Investigator, may continue on NRTI treatment following discussion with the Sponsor Medical Monitor to document the rationale for continuing NRTI.

Participants who do not qualify for NRTI discontinuation will continue taking the NRTI until the end of the Follow-Up Period. Once a participant has completed the study, long-term care should be determined by the Investigator or primary treating physician based on local clinical guidelines.

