4. STATISTICAL ANALYSES

4.1. General Considerations

All analyses will use SAS version 9.4 or higher. The schedule of study assessments and time points are provided in the current PREVAIL master protocol and STRIVE sub-study.

Data will be provided in by-participant listings for the All Enrolled Set, unless otherwise specified.

Efficacy endpoints will be summarized by TDF/TD discontinued (participants who discontinued TDF/TD when the TDF/TD discontinuation criteria were met in the Follow-up period) and overall for each cohort.

Continuous variables will be summarized using the following descriptive summary statistics: the number of participants (n), mean, standard deviation (SD), median, Q1 (first quartile), Q3 (third quartile), minimum value (min), and maximum value (max), unless otherwise specified. In general, the precision of the measurement for each continuous variable will be used to determine the number of decimal places to present in tables, figures, and derived listings. Minimum and maximum values will be reported with the same precision as the units of measure. The mean and median will be reported to 1 additional decimal place, and the SD will be reported to 2 additional decimal places. Any values that require transformation to standard units (metric or SI) will be converted with the appropriate corresponding precision.

Categorical variables will be summarized using counts and percentages. Percentages will be rounded to one decimal place, except 100% will be displayed without any decimal places, and percentages will not be displayed for zero counts.

Baseline value: Unless otherwise specified, the baseline value will be defined as the most recent non-missing (scheduled or unscheduled) measurement collected prior to the initial administration of study intervention. If baseline cannot be determined due to missing data, no derivation will be performed, and baseline will be set to missing.

Change (absolute change) from baseline will be calculated as post-baseline value – baseline value.

Study day: The study day of an event/measurement is defined as the relative day of the event/measurement starting with the date of the first study drug administration (reference date) as Day 1 (there will be no Day 0).

The study day of event/measurement occurring before the first study drug administration will be calculated as:

$$\text{Study Day} = (\text{Date of event/measurement} - \text{Date of first study drug administration})$$

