For event/measurement occurring on or after Day 1, the study day will be calculated as:

$$\text{Study Day} = (\text{Date of event/measurement} - \text{Date of first study drug administration}) + 1.$$

End of treatment (EOT) date: EOT date is the date of the last dose of VIR-2218, VIR-3434 and PEG-IFNa.

EOT assessment: The earliest available assessment on or after EOT date.

EOT + 24 weeks assessment: The earliest available assessment on or after EOT + 161 days.

Treatment Period and Follow-Up Period: Treatment Period and Follow-Up Period are defined in the protocol.

Treatment-emergent (TE) Period: The TE Period is defined as the time period on or from the start of study intervention(s) until the last dose of VIR-2218 + 30 days, or VIR-3434 + 24 weeks, or PEG-IFN α + 30 days, or TDF/TD + 30 days, whichever is later. The TE Period will be used for safety analysis.

Post-TE Period: The Post-TE Period is defined as the time period after the TE Period through the end of Follow-Up Period.

Analysis windows: The analysis window rules for protocol-defined visits are provided in [Appendix 2](#).

Unscheduled visits: Unscheduled visit measurements will be included in the analysis as follows:

1. In planned visit windows as specified, the analysis window rules described in [Appendix 2](#), if applicable.
2. In the derivation of the baseline.
3. In the derivation of maximum and minimum values, or maximum and minimum change from baseline values during the Treatment Period and Follow-Up Period for efficacy analyses, or worst values/grades during the TE Period for safety analyses.
4. In individual participant data listings as appropriate.

Repeated observations: Measurements recorded at different time points are defined as repeated observations. If an assessment has planned repeated measurements, then statistical summaries will present all planned time points, as appropriate.

If there are multiple records at a single assessment date, regardless of whether scheduled or unscheduled visit, the latest record will be used for the analysis.

Missing data handling conventions:

- Missing data can occur due to study withdrawal or participants lost to follow-up before the completion of the study or due to intermittent missing values (i.e., data between two non-missing assessments).
- Missing data in the by-participant data listings will be presented as missing.

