
9. Proportion of participants achieving sustained suppression of HBV DNA (< LLOQ) with HBsAg loss (< 0.05 IU/mL) after discontinuation of all treatment:
 
a. at 24 weeks
 
b. at the F48 Follow-Up visit
 
11. Proportion of participants achieving sustained suppression of HBV DNA (< LLOQ) after discontinuation of all treatment:
 
a. at 24 weeks
 
b. at the F48 Follow-Up visit
	
Due to early study termination, modification to timepoints of a. and b. as below:
 
a) at 24 weeks after discontinuation of all treatments (an analysis window of 168 ± 14 days will be applied to capture data around the 24 weeks timepoint, following the rules in Appendix 2 for data selection)
 
b) at the last Follow-Up visit, for participants who have > 24 weeks of discontinuation, after discontinuation of all treatments
 
c) at the last Follow-Up visit after discontinuation of all treatments (all participants will be included in the denominator)
 
Specifically, for a) and b), the denominator used in the percentage calculation will exclude participants with uncertain NRTI discontinuation status due to early study termination (e.g., no Follow-Up 12 visit).
 
The number and percentage of participants achieving
 
 • sustained suppression of HBV DNA (< LLOQ) • sustained suppression of HBV DNA (< LLOQ) with HBsAg loss (< 0.05 IU/mL) 
will be summarized by cohort with the two-sided 95% Clopper-Pearson CI.
 
In addition, the number and percentage of participants achieving
 
 • sustained suppression of HBV DNA (< LLOQ), allowing transient viremia

	
 • sustained suppression of HBV DNA (< LLOQ) with HBsAg loss (< 0.05 IU/mL), allowing transient viremia where transient viremia is defined as HBV DNA \geq LLOQ or HBsAg \geq LLOQ for \leq 35 days, adapted from the 2022 American Association for the Study of Liver Diseases (AASLD) – The European Association for the Study of the Liver (EASL) functional cure definition (AASLD-EASL, 2022), will be analyzed similarly. 
Similarly, the analyses above will be repeated after replacing “HBsAg loss (<0.05 IU/mL) with “HBsAg < 100 IU/mL”. Accordingly, the transient viremia is defined as HBV DNA \geq LLOQ or HBsAg \geq 100 IU/mL for \leq 35 days, adapted from the 2022 AASLD-EASL partial functional cure definition (AASLD-EASL, 2022).

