Analysis Window	< D1 dose time			≥D1 dose time, +28		±28		-28, +42			±42			-42, +14		-14, EOT Date	
CLDQ-HBV, WPAI:GH																	

Table 11: Analysis Windows for Safety, Efficacy, and other Assessments: Follow-Up Period for Participants Who Never Discontinue NRTI during Follow-Up Period

Study Stage	Follow-Up Period								
	Follow up Visit	F1	F4	F8	F12	F16	F20	F24	F36
Visit Day ± Visit Window	D8 ±2	D29 ±7	D57 ±7	D85 ±7	D113 ±7	D141 ±7	D169 ±7	D253 ±7	D337 ±7
Analysis Visit	FU Week 1	FU Week 4	FU Week 8	FU Week 12	FU Week 16	FU Week 20	FU Week 24	FU Week 36	FU Week 48/EOFU
Analysis Window	EOT DATE , +7	±14	±14	±14	±14	±14	-14, +42	±42	-42, +14
HBV DNA quantification, HBsAg quantitative, Liver function tests, Serum chemistry, Hematology, Coagulation parameters, Anti-HBs quantitative, HBeAg quantitative, Anti-HBe qualitative.									
Analysis Visit	FU Week 1	FU Week 4		FU Week 12			FU Week 24		FU Week 48/EOFU
Analysis Window	EOT DATE , +7	-14, +28		-28, +42			-42, +84		-84, +14
HBcrAg, HBV RNA.									
Analysis Visit	FU Week 1			FU Week 12			FU Week 24		FU Week 48/EOFU
Analysis Window	EOT DATE , +35			±42			-42, +84		-84, +14
CLDQ-HBV, WPAI:GH.									

Table 12: Analysis Windows for Safety, Efficacy, and other Assessments: Follow-Up Period for Participants Who Discontinue NRTI at F1

Study Stage	Follow-Up Period															
	Follow up Visit	F1	F2	F4	F6	F8	F10	F12	F16	F20	F24	F28	F32	F36	F40	F44

Visit Day ± Visit Window	D8 ±2	D15 ±2	D29 ±7	D43 ±7	D57 ±7	D71 ±7	D85 ±7	D113 ±7	D141 ±7	D169 ±7	D197 ±7	D225 ±7	D253 ±7	D281 ±7	D309 ±7	D337 ±7
Analysis Visit	FU Week 1	FU Week 2	FU Week 4	FU Week 6	FU Week 8	FU Week 10	FU Week 12	FU Week 16	FU Week 20	FU Week 24	FU Week 28	FU Week 32	FU Week 36	FU Week 40	FU Week 44	FU Week 48/EOFU
Analysis Window	EOT DATE ,+2	-5, +7	±7	±7	±7	±7	-7, +14	±14	±14	±14	±14	±14	±14	±14	±14	±14
HBV DNA quantification, HBsAg quantitative, Liver function tests, Serum chemistry, Hematology, Coagulation parameters, Anti-HBs quantitative, HBeAg quantitative, Anti-HBe qualitative.																
Analysis Visit	FU Week 1		FU Week 4				FU Week 12			FU Week 24						FU Week 48/EOFU
Analysis Window	EOT DATE ,+7		-14, +28				-28, +42			-42, +84						-84, +14
HBcrAg, HBV RNA.																
Analysis Visit	FU Week 1						FU Week 12			FU Week 24						FU Week 48/EOFU
Analysis Window	EOT DATE ,+35						±42			-42, +84						-84, +14
CLDQ-HBV, WPAI:GH.																

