Table 13: Analysis Windows for Safety, Efficacy, and other Assessments: Follow-Up Period for Participants Who Discontinue NRTI at F12

Study Stage	Follow-Up Period															
Follow up Visit	F1	F4	F8	F12	F14	F16	F18	F20	F22	F24	F28	F32	F36	F40	F44	F48/EOFU
Visit Day ± Visit Window	D8 ±2	D29 ±7	D57 ±7	D85 ±7	D99 ±7	D113 ±7	D127 ±7	D141 ±7	D155 ±7	D169 ±7	D197 ±7	D225 ±7	D253 ±7	D281 ±7	D309 ±7	D337 ±7
Analysis Visit	FU Week 1	FU Week 4	FU Week 8	FU Week 12	FU Week 14	FU Week 16	FU Week 18	FU Week 20	FU Week 22	FU Week 24	FU Week 28	FU Week 32	FU Week 36	FU Week 40	FU Week 44	FU Week 48/EOFU
Analysis Window	EOT DATE ,+7	±14	±14	-14, +7	±7	±7	±7	±7	±7	-7, +14	±14	±14	±14	±14	±14	±14

HBV DNA quantification, HBsAg quantitative, Liver function tests, Serum chemistry, Hematology, Coagulation parameters, Anti-HBs quantitative, HBeAg quantitative, Anti-HBe qualitative.													
Analysis Visit	FU Week 1	FU Week 4		FU Week 12					FU Week 24				FU Week 48/EOFU
Analysis Window	EOT DATE , +7	-14, +28		-28, +42					-42, +84				-84, +14
HBcrAg, HBV RNA.													
Analysis Visit	FU Week 1			FU Week 12					FU Week 24				FU Week 48/EOFU
Analysis Window	EOT DATE , +35			±42					-42, +84				-84, +14
CLDQ-HBV, WPAI:GH.													

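### In the STRIVE SAP, the by-visit HBV DNA and ALT summaries for people who stopped TDF/TD pool two stop times 11 weeks apart, because follow-up weeks are counted from the last injection

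*SAP*

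**What the plan says.** All points below are from the STRIVE SAP.

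- **Stop times.** Section 1.2.4: "Participants will discontinue NRTI at F1 or at F12 Follow-Up visits based on the most recent data available", provided that four criteria are met.
- **Follow-up clock.** Section 4.1: "EOT date is the date of the last dose of VIR-2218, VIR-3434 and PEG-IFNa". TDF/TD is not part of the definition. In Appendix 2 the first follow-up window starts at the EOT date both in Table 12 ("Analysis Windows for Safety, Efficacy, and other Assessments: Follow-Up Period for Participants Who Discontinue NRTI at F1") and in Table 13 ("Follow-Up Period for Participants Who Discontinue NRTI at F12"), and the two tables use the same FU Week labels.
- **Reporting group.** Section 4.1: "Efficacy endpoints will be summarized by TDF/TD discontinued" and overall, for each cohort. No split by stop visit is stated.
- **By-visit endpoints affected.** HBV DNA below LLOQ and ALT at or below ULN (Section 4.4.1, secondary endpoints 15 and 16), and HBV DNA level and change (Section 4.5.1, exploratory endpoint 9).
- **Extra visits.** Section 1.2.3 gives F1 stoppers "additional visits at F2, F6, F10, F28, F32, F40, and F44" and F12 stoppers "additional visits at F14, F18, F22, F28, F32, F40, and F44".
- **Sustained suppression.** For secondary endpoints 9 and 11, Section 4.4.1 counts 24 weeks from discontinuation of all treatments: "an analysis window of 168 ± 14 days will be applied to capture data around the 24 weeks timepoint". The two last-visit timepoints also refer to discontinuation of all treatments.

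**The concern.** A by-visit column for people who stopped NRTI will be read as a picture of what happens after NRTI is withdrawn: how long HBV DNA stays below LLOQ, whether ALT stays normal, and when either changes. For that, the rows should represent time off NRTI. Here they represent time since the last injection. For F1 stoppers the two clocks differ by one week; for F12 stoppers they differ by twelve. A pooled row can therefore combine suppression maintained by TDF/TD, or only just tested after stopping it, with results from people who have been off it for months. F12 stoppers must also have HBV DNA below LLOQ on the latest data when they stop, so their suppression around FU Week 12 is largely a condition of entering the group.

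**Working it through.** **Inputs (Appendix 2, Tables 12 and 13).** F1 is follow-up Day 8 (±2) and F12 is Day 85 (±7). Each nominal visit day equals 7 × FU week + 1. I assume that TDF/TD stops on the nominal F1 or F12 day.

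**Gap between stop times.** 85 − 8 = 77 days = 11 weeks. At the edges of the visit windows it runs from 78 − 10 = 68 days to 92 − 6 = 86 days (9.7 to 12.3 weeks).

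**Which weeks are shared.** In the HBV DNA and laboratory rows the two tables name 19 distinct FU weeks. Thirteen are in both: 1, 4, 8, 12, 16, 20, 24, 28, 32, 36, 40, 44 and 48. Weeks 2, 6 and 10 occur only in Table 12; weeks 14, 18 and 22 only in Table 13.

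**Time off NRTI in shared weeks** (visit day − 8 for F1 stoppers; visit day − 85 for F12 stoppers):

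| FU Week | Day | F1 stoppers | F12 stoppers |
|---|---|---|---|
| 1 | 8 | 0 | on TDF/TD |
| 4 | 29 | 21 d = 3 wk | on TDF/TD |
| 8 | 57 | 49 d = 7 wk | on TDF/TD |
| 12 | 85 | 77 d = 11 wk | 0 |
| 16 | 113 | 105 d = 15 wk | 28 d = 4 wk |
| 24 | 169 | 161 d = 23 wk | 84 d = 12 wk |
| 36 | 253 | 245 d = 35 wk | 168 d = 24 wk |
| 48 | 337 | 329 d = 47 wk | 252 d = 36 wk |

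**Check on endpoints 9 and 11.** Counted from the NRTI stop, 168 days falls on follow-up Day 8 + 168 = 176 for F1 stoppers (window 162 to 190, which includes F24 on Day 169). For F12 stoppers it falls on Day 85 + 168 = 253, which is F36. These endpoints compare like with like.

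**Illustration of the blurring (assumed figures only).** Suppose that half stop at F1 and half at F12, that everyone rises above LLOQ a fixed time after stopping, that nobody is retreated, and that each row counts those with a visit scheduled.

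- Rebound at 6 weeks: the column shows 50% suppressed at FU Weeks 8, 12 and 16.
- Rebound at 8 weeks: 50% at FU Weeks 12 and 16.
- Rebound at 12 weeks: 50% at FU Weeks 16 and 20.

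By time off NRTI the figure is 0% from the rebound week on in all three cases. With another split, 50% becomes whatever share stopped at F12. In the 8-week case the rows at FU Weeks 8, 10, 12, 14, 16, 18 and 20 read 100, 0, 50, 100, 50, 100 and 0%, because the single-group rows alternate between different people.

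**Can the visits be matched on time off NRTI?** F1 stoppers' F2, F4, F6, F8, F10, F12, F16, F20, F24, F28, F32 and F36 fall 1, 3, 5, 7, 9, 11, 15, 19, 23, 27, 31 and 35 weeks off. F12 stoppers' F14, F16, F18, F20, F22, F24, F28, F32, F36, F40, F44 and F48 fall 2, 4, 6, 8, 10, 12, 16, 20, 24, 28, 32 and 36 weeks off. All twelve pairs agree within one week. In each pair, time since the last injection differs by 12 weeks (F2 against F14, for example).

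**The case against.** The strongest reply is that the main question is already handled. Sustained suppression after stopping everything is the subject of secondary endpoints 9 and 11, and every timepoint for them in Section 4.4.1 refers to discontinuation of all treatments. A reader might infer that the off-treatment endpoints in general use the wrong clock; the documents do not support that. Secondary endpoints 3, 8 and 10b are defined relative to EOT, so an EOT clock is right for them. What remains is descriptive, in a study without hypothesis tests.

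Second, individual HBsAg, ALT and HBV DNA values are plotted at each visit (Sections 4.4.1 and 4.5.1), and values and NRTI stop and retreatment status are listed by participant. With few stoppers per cohort, these would let a careful reader reconstruct rebound times. This limits the harm, but the tabulated column would still be read as it stands.

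Third, it would be wrong to move everything to the NRTI-stop clock. Protocol Section 4.2.2 says that NRTIs do not directly affect HBsAg production. Section 4.3.1 gives VIR-3434 a half-life of about 25 days, with measurable levels for up to 24 weeks after a single dose in healthy volunteers. For HBsAg, time since the last injection is the defensible axis; re-anchoring would put people 12 weeks apart in antibody washout on one row. This stands, and it confines the point to HBV DNA and ALT.

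Two further readings go too far. One is that every follow-up week mixes the groups: six of 19 hold only one group, and the 11-week difference in time off applies only from FU Week 12. The other is that suppression will be overstated. The 50% against 0% contrast rests on an assumed split and universal rebound at a fixed time. Retreated participants also stay in follow-up (Section 1.2.5), so later rows could be shifted in the other direction.

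**Conclusion.** The point holds for the by-visit HBV DNA and ALT summaries of the pooled TDF/TD-discontinued group. In the shared weeks that group combines F1 stoppers with F12 stoppers who are still on TDF/TD (FU Weeks 4 and 8) or who are 77 days less far off it (FU Week 12 onward). The column does not separate on-treatment from off-treatment suppression, and it blurs the time of rebound. The documents do not fix the direction or size of any distortion.

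The primary endpoint at EOT and the sustained-suppression endpoints are unaffected. The week counts assume stopping on the nominal visit day; a later actual stop shifts them. The point concerns STRIVE only. The supplied protocol is for THRIVE, where TDF ends with the last dose of the injected agents (Section 4.3.3), so two NRTI stop times do not arise. The STRIVE protocol and table shells were not available, and a split by stop visit may be planned there.

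**What to change.** 1. For HBV DNA below LLOQ, HBV DNA level and change, and ALT in the TDF/TD-discontinued group, add by-visit tables and figures on weeks since the last TDF/TD dose: 2, 4, 6, 8, 10, 12, 16, 20, 24, 28, 32 and 36, using the visit pairs shown above. Keep F1 stoppers' F40, F44 and F48 as further rows (nominally 39, 43 and 47 weeks off; label them about 40, 44 and 48), so that the longest off-treatment data are not lost.
2. Keep the EOT-anchored windows for HBsAg and for the overall column. Split the EOT-anchored discontinued column by stop visit, F1 and F12.
3. Leave secondary endpoints 3, 8, 9, 10b and 11 as defined.

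The cost is some SAP wording and one more set of descriptive outputs from data already scheduled for collection. Numbers per row will be small. Each re-anchored row keeps a 1-week difference in time off NRTI and about 12 weeks' difference in time since the last injection; a footnote should state both.

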APPENDIX 3. IMPUTATION RULE FOR MISSING/PARTIAL PRIOR/CONCOMITANT MEDICATION DATES

In principle, if a medication cannot be determined as prior, concomitant, or both, it will be classified as both and summarized in both prior medication and concomitant medication. Imputation rules for partial medication dates (D = day, M = month, Y = year):

1. Missing or partial medication start date:
 - a. If only D is missing, use the first day of the month.
 - b. If D and M are both missing, use the first day of the year.
 - c. If D, M and Y are all missing, use the informed consent date.
2. Missing or partial medication stop date:
 - a. If only D is missing, use the last day of the month.
 - b. If D and M are both missing, use the last day of the year.
 - c. If D, M and year are all missing, assign ‘ongoing’ status to stop date.

In summary, the prior and concomitant categorization of a medication is described below.

Table 14: Prior and Concomitant Categorization of Medication

Medication Start Date	Medication Stop Date	
	< First Dose Date of Study Drug	≥ First Dose Date
< First dose date of study drug	P	PC
≥ First dose date	-	C

P: Prior; C: Concomitant

